**Proprietary confidential information.**

**© 2016 Boehringer Ingelheim International GmbH or one or more of its affiliated companies. All rights reserved.**

This document may not - in full or in part - be passed on, reproduced, published or otherwise used without prior written permission.

- The patient is no longer able to participate for other reasons (e.g. adverse events unrelated to therapy or disease progression, concomitant diagnoses, pregnancy, surgery or administrative reasons). The investigator may also stop a patient's participation if the patient is unable to attend trial visits

A patient can be withdrawn after discussion between the investigator and the clinical monitor at Boehringer Ingelheim if eligibility criteria are violated and/or the patient fails to comply with the protocol.

All withdrawals will be documented and the reason for withdrawal recorded and discussed, as necessary, in the final report of the trial. As soon as a patient is withdrawn from the trial, the EOT has to be performed if feasible ([see Flowchart for Course 3](#)). Every effort should be made to follow-up patients in case an AE is still ongoing at the time of withdrawal.

Patients who have not completed at least two administrations will be replaced at the same dose level.

Patients who terminate trial treatment due to DLT will not be replaced.

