#### 4.1.3 Selection of doses in the trial

BI 836826 will be administered as a rate-controlled, intravenous infusion..

A fixed dose of 1 mg BI 836826 per patient is expected to be the safe first in human starting dose for patients with an advanced haematological malignancy. The calculation of the safe starting dose of 1 mg in humans was based on data from studies in cynomolgus monkeys and from *ex vivo* experiments with primary B cells obtained from fresh blood samples of CLL patients. This dose is anticipated to represent a low pharmacologically active dose which may be capable to result in a detectable B cell reduction in the peripheral blood. For details please refer to the Investigator's Brochure, section 5.3.6 ([c01715907-08](#)).

Proprietary confidential information.

© 2016 Boehringer Ingelheim International GmbH or one or more of its affiliated companies. All rights reserved.

This document may not - in full or in part - be passed on, reproduced, published or otherwise used without prior written permission.

The dose was planned to be escalated in cohorts at predefined dose levels based on a multiplication factor of approximately 3 in the low dose range (1-25 mg), a factor of 2 at doses of 25-800 mg and from the dose of 800 mg and onwards additional 200 mg per dose. The dose levels were initially planned to be: 1 mg, 3 mg, 9 mg, 25 mg, 50 mg, 100 mg, 200 mg, 400 mg, 800 mg, 1000 mg, 1200 mg and 1400 mg, however the MTD was established at 100mg based on safety data from Caucasian patients. An additional cohort of Korean patients will be tested at 50 and 75mg. Every time a dose-escalation is to be performed, all patients at the last cohort must have had 2 infusions of BI 836826 and at least 7 days observation after the second infusion. The available data of all previous dose cohorts will be reviewed. The data will be provided to the DSMB who will be asked to provide an independent assessment including the dose recommendation for the next cohort. As a result, lower dose increments than the predefined levels will be possible.

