#### **5.2.1.1 Dose limiting toxicity**

Dose limiting toxicity (DLT) is defined as any drug-related non-haematological adverse event CTCAE grade 3 or higher, except infusion-related reactions associated with the administration of BI 836826.

Complications resulting from haematological adverse events, e.g. bleeding due to thrombocytopenia or infection due to neutropenia are classified as non-haematological adverse events and are covered by the above definition of DLT. Nevertheless, haematological adverse events, e.g. neutropenia, thrombocytopenia and anemia will be considered for definition of the dose for further development.

The MTD will be defined on the basis of DLT observed during the first 2 weeks of the first treatment course. In case of a delay of the second administration, evaluation of DLT should be prolonged to 7 days after the second administration. However, for those patients who receive more than two doses of BI 836826, all adverse events corresponding to the above definition of DLT will be considered for the purpose of confirming the MTD and for the selection of the recommended dose for treatment of the expansion cohort and for further development. In regular intervals, all available safety data including adverse events qualifying for DLT will be submitted to the DSMB. The DSMB will independently assess this information and provide recommendations for trial conduct and dose-escalation.

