5. ENDPOINTS

5.1 PRIMARY ENDPOINTS

The primary endpoints of this trial are the MTD and the number of dose limiting toxicities (DLTs) during the MTD evaluation period. Instead of the MTD, an OBD might be defined instead.

Maximum tolerated dose (MTD):

MTD is defined as the highest dose studied for which the incidence of DLTs is no more than 17% (i.e., 1/6 patients) during the MTD evaluation period.

The MTD evaluation period is defined as the time from the first administration of study medication to 7 days after the second administration.

Note that in case of administration of split dose during course 1, both infusions on consecutive Days 1 and 2 of Course 1 are considered as the first administration.

Additionally, all information, including adverse events (AEs) qualifying for a DLT from later times, will be considered in the final determination of the dose recommended for Phase II.

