7.4 PRIMARY ENDPOINTS

The primary endpoints of this trial are the MTD and the number of DLTs during the MTD evaluation period. The MTD is determined from the occurrences of DLTs during the MTD evaluation period, which is from treatment start until the second infusion of BI 836826 plus 7 days. An overall summary of the DLTs (see CTP Section 5.2.1.1 for definitions of DLT)

which occurred during the MTD evaluation period will be provided for each dose cohort. Patients, if any, who did not complete at least two administrations of BI 836826 for reasons other than DLT will be excluded from the analysis of the primary endpoint. These patients will be replaced at the same dose level.

At the end of the dose escalation phase, a brief interim safety analysis was performed and reported to further describe the dose escalation steps actually occurred and to justify the determination of MTD, see also [Section 9.1](#) and “CTR – Phase I Safety Analysis Report” ([8](#)).

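### Replacement and MTD evaluability are keyed to two administrations, not to the DLT window, so a patient lost to observation in the 7 days after infusion 2 stays in the primary denominator with no DLT

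*Protocol*

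**What the plan says.** Four rules bear on the same patient.

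- **Window.** SAP section 5.1 has the MTD evaluation period "defined as the time from the first administration of study medication to 7 days after the second administration". Protocol section 5.2.1.1 agrees when infusion 2 is late: "In case of a delay of the second administration, evaluation of DLT should be prolonged to 7 days after the second administration".
- **Escalation.** Protocol section 4.1.3 requires, before each step up, that "all patients at the last cohort must have had 2 infusions of BI 836826 and at least 7 days observation after the second infusion".
- **Replacement.** Protocol section 3.3.4.1 says: "Patients who have not completed at least two administrations will be replaced at the same dose level". It adds: "Patients who terminate trial treatment due to DLT will not be replaced".
- **Primary-endpoint exclusion.** For the primary-endpoint analysis, the rule in SAP section 7.4 is that patients "who did not complete at least two administrations of BI 836826 for reasons other than DLT will be excluded". The section goes on to provide for their replacement within the same dose level.

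The first two rules refer to the 7 days after infusion 2. The last two do not.

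**The concern.** The primary endpoints are the MTD and the number of DLTs in the evaluation period, read from cohorts of three to six patients. A patient whose window was cut short has not been shown to be free of DLT. If that patient fills one of six places, the cohort's DLT rate is biased low, in the direction of accepting the dose. The issue is live: SAP section 3 aims to define an MTD in Korean patients, after three of four Korean patients at 100 mg developed significant toxicities.

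The event is also foreseeable. Protocol section 3.3.4.1 lets patients leave at any time, and SAP section 9.1.1 timed the interim safety analysis for when each dose-finding patient had finished the evaluation period or dropped out.

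**Working it through.** **The plan's own figure.** The MTD criterion in SAP section 5.1 is a DLT incidence of at most 17%, given as 1 of 6. 1/6 = 16.7%, which rounds to 17%, so it reproduces.

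**One patient traced through the rules.** Infusion 2 is given on day 8, consent is withdrawn on day 10, and no DLT has been seen.

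1. Protocol 4.1.3: 7 days of observation after infusion 2 can never be reached, so read literally the patient blocks escalation.
2. Protocol 3.3.4.1: two administrations were completed, so replacement is not required.
3. SAP 7.4: two administrations were completed, so the patient is not excluded.
4. SAP 6.6 and Protocol 7.4: no imputation applies to the unseen days.

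The result is one more in the denominator and none in the numerator. Where no further escalation is planned, step 1 drops out and SAP 7.4 alone decides who counts. Examples are the 75 mg Korean cohort, the highest dose planned for these patients, and a dose filled to six to confirm the MTD.

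**Size, as an illustration.** Assumptions, none of them in the documents: true window DLT risk p of 17%, 25% or 33%; constant hazard; exactly one leaver, in the first three patients; share f of the window risk observed in that leaver from 0.5 (leaves just after infusion 2) to 0.9 (leaves near the end of the window). A dose passes the 3+3 rule with 0 DLTs in 3, or 1 in 3 followed by 0 in 3.

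- Complete windows: pass = (1−p)^3 + 3p(1−p)^2 × (1−p)^3.
- One leaver, whose detectable risk is s = 1 − (1−p)^f: pass = P0 + P1 × (1−p)^3, with P0 = (1−p)^2 × (1−s) and P1 = 2p(1−p)(1−s) + (1−p)^2 × s.

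For p = 0.33 with complete windows: 0.301 + 0.444 × 0.301 = 0.434.

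For p = 0.33 and f = 0.5: s = 1 − 0.67^0.5 = 0.181, P0 = 0.449 × 0.819 = 0.367, P1 = 0.443, and pass = 0.367 + 0.443 × 0.301 = 0.501.

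| True DLT risk | Complete | One leaver, f = 0.5 | One leaver, f = 0.9 | Rise in points |
|---|---|---|---|---|
| 17% | 0.773 | 0.810 | 0.780 | 0.7 to 3.7 |
| 25% | 0.600 | 0.656 | 0.610 | 1.0 to 5.6 |
| 33% | 0.434 | 0.501 | 0.447 | 1.3 to 6.7 |

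For the chance of 0 DLTs in 3 at p = 0.33, complete windows give 0.67^3 = 30%. A leaver with 8 of 14 days observed gives 0.67^(2+8/14) = 36%, and one with 13 of 14 days gives 31%. The ceiling, departure immediately after infusion 2, is 0.67^2.5 = 37%.

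**The case against.** Several points on the other side stand and limit the scope.

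- **Stopping drug is not leaving observation.** Protocol section 5.2.2.2 collects all adverse events, and all deaths, until 8 weeks after the last administration. A reader might infer that anyone who progresses to other therapy or dies of lymphoma in that week also has unobserved time. The documents do not support this. Starting other therapy does not by itself end adverse event collection, and a patient who dies is observed until death, which is a competing event. The clear cases are consent withdrawal and loss to follow-up.
- **Escalation is protected.** Protocol section 4.1.3 withholds the step up, and the data go to the DSMB. A reader might infer that earlier escalations, or the 100 mg MTD in Caucasian patients, rest on incomplete windows. Nothing in the documents shows that any such patient existed.
- **The count does not set the MTD mechanically.** SAP section 7.8 foresees no model, only a descriptive listing by dose group. Protocol section 5.2.1.1 also considers later DLT-type events, and section 7.4 asks for every effort to complete data on potential DLTs. A leaver would probably be visible.
- **The rules are not strictly incompatible.** Section 3.3.4.1 says who must be replaced and bars replacement only for DLT terminations. It does not forbid an extra patient. It simply offers no stated way forward.
- **That the leaver counts as DLT-free is an inference.** It follows from non-exclusion and non-imputation; no sentence says it.

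None of this supplies an evaluability rule that matches the window.

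**Conclusion.** The mismatch is real and should be corrected. The replacement and exclusion rules stop at the second administration, while the window and the escalation condition run 7 days further. A patient lost to observation in that week without a DLT is counted in the SAP 7.4 denominator with an incomplete window, and under Protocol 4.1.3 blocks escalation with no stated resolution. The practical exposure is mainly in cohorts with no escalation after them.

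The direction favours tolerability. The size is about 1 to 7 points of 3+3 pass probability, conditional on one leaver in the first three patients and on the assumed risks and observed shares. With no leaver rate in the documents, the unconditional effect is unknown and may be very small.

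A reader might infer that one leaver turns a passing 1/6 (16.7%) into a failing 1/5 (20.0%). That holds only if the leaver is removed and not replaced. With replacement the cohort returns to six, so 1/5 is an unfinished cohort rather than a failed dose.

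**What to change.** Use one definition in Protocol section 3.3.4.1 and SAP section 7.4. A patient is MTD-evaluable if he or she had a DLT in the MTD evaluation period, or received two administrations and was observed for DLT until 7 days after the second.

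- Patients who only stop drug but are still followed for adverse events remain evaluable.
- State how a death without DLT inside the window is counted.
- Non-evaluable patients are replaced and left out of the primary denominator, but stay in all Treated Set safety tables.

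If the protocol is not reopened, change SAP section 7.4 alone and report the DLT rate among fully observed patients. SAP section 6.3 has the list of replaced patients settled by the last report planning meeting before database lock, which is a natural point to identify any such patient.

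The cost is a sentence or two in each document and occasionally one more patient in a cohort, or a slightly smaller denominator under the SAP-only route. If no patient was lost in that week, no result changes.

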### **3.3.4.2 Discontinuation of the trial by the sponsor**

Boehringer Ingelheim reserves the right to discontinue the trial overall or at a particular trial site at any time for the following reasons:

1. Violation of GCP, the clinical trial protocol (CTP), or the contract by a trial site or investigator, disturbing the appropriate conduct of the trial
2. Emergence of any efficacy/safety information that could significantly affect continuation of the trial
3. Failure to meet expected enrolment goals overall or at a particular trial site

The investigator / the trial site will be reimbursed for reasonable expenses incurred in case of trial termination (except in case of the first reason).

## 4. TREATMENTS

### 4.1 TREATMENTS TO BE ADMINISTERED

BI 836826 will be administered as an intravenous infusion. The first course of treatment has a duration of 7 weeks which starts with one infusion weekly 4 times followed by 27 days of observation after the 4th infusion ([Figure 3.1:1](#)), unless the split first dose administration described below will be implemented. A second course similar to course 1 can be administered, if the drug is well tolerated and the patient has no clinical signs of progression, judged by the treating physician. An additional third course of 4 weekly administrations can be given to the patients with response (*i.e.* complete or partial remission) and patients with stable disease, who tolerate the drug well and have clinical benefit. Clinical benefit can be improvement of clinical symptoms, and/or reduction in tumour size not meeting the criteria for a partial remission at the response assessment at the end of the second course.

The first infusion in each course should be started at a rate of 10 mL/h. The infusion rate can be increased every 30 (+/-10) minutes by 10 mL/h to a maximum of 80 mL/h as long as tolerated by the patient. If considered safe by the investigator, the subsequent infusions may be given with shorter interval for increasing the rate, but the maximum rate should not exceed 120 mL/h.

If adverse events which are considered related to the infusion schedule, *e.g.* infusion-related reaction, are not well controlled by the above schedule an alternative administration will be used. The first administration in course 1 will be split into two infusions, a low dose on day 1 followed by the full dose on the day 2. The first part of the administration will be 10% of the full dose, but not exceeding 10 mg given on day 1. The day after the second part of the administration will be the full planned dose for the patient (please refer the flowchart in [section 10.7](#)). The same infusion schedule should be employed as described above, starting with a rate of 10 mL/h. Premedication is mandatory before both infusions as they will be considered as the first administration ([section 4.1.4.1.1](#)). The potential change of the first infusion into two infusions will be assessed and may be modified by the DSMB. In subsequent administrations, the full dose of BI 836826 will be administered as a rate-controlled intravenous infusion on day 1.

If symptoms of an infusion related reaction occur, the infusion should be temporarily stopped. Upon recovery, it should be resumed at 50% of the rate at which the reaction occurred for at least 30 minutes. Lower rates may be selected if clinically indicated. Depending on the time of occurrence and the severity of the reaction, the investigator may consider administering additional supportive medication, *e.g.* corticosteroids. A stepwise re-increase of the infusion rate to a maximum of 80 mL/h is possible.

For medical reason, the duration of the infusion may be expanded until the use-by date and use-by time indicated on the label is reached. The actual duration of the infusion needs to be documented in the eCRF including actual start and end time, actual time points for interruption and restart of the infusion and the actual infusion rates.

Proprietary confidential information.

© 2016 Boehringer Ingelheim International GmbH or one or more of its affiliated companies. All rights reserved.

This document may not - in full or in part - be passed on, reproduced, published or otherwise used without prior written permission.

Adverse events during the infusion should be thoroughly documented and characterized to allow differentiation between infusion-related reactions and tumour lysis syndrome ([R10-4428](#), [R10-4517](#)).

#### 4.1.1 Identity of BI investigational product and comparator product

Substance (INN):	BI 836826
Pharmaceutical form:	Solution for infusion after dilution
Source:	Boehringer Ingelheim Pharma GmbH & Co. KG
Unit strength:	10 mg/mL (vials with 10 mL)
Daily dose:	See section 4.1.3
Duration of use:	Single dose or split dose (2 doses) only applicable for course 1 once weekly for 4 times followed by 27 days of observation after last administration, i.e 7 weeks = course 1. A similar additional course 2 can be given, if drug is well tolerated and no signs of progression. For patients with remission or stable disease with clinical benefit additional weekly infusion for 4 times followed by 55 days of observation can be administered (course 3). Maximum 12 infusions = 3 courses. Further infusions only after agreement between sponsor and investigator on a case by case
Route of administration:	Intravenous
Posology:	Rate controlled infusion See Section 4.1.6

#### 4.1.2 Method of assigning patients to treatment groups

This is a single arm, open-label, dose-escalation trial. Assignment of a patient to a dose has to be confirmed by the investigator with the clinical monitor of the sponsor as described below in sections [4.1.3](#) and [4.1.4](#).

#### 4.1.3 Selection of doses in the trial

BI 836826 will be administered as a rate-controlled, intravenous infusion..

A fixed dose of 1 mg BI 836826 per patient is expected to be the safe first in human starting dose for patients with an advanced haematological malignancy. The calculation of the safe starting dose of 1 mg in humans was based on data from studies in cynomolgus monkeys and from *ex vivo* experiments with primary B cells obtained from fresh blood samples of CLL patients. This dose is anticipated to represent a low pharmacologically active dose which may be capable to result in a detectable B cell reduction in the peripheral blood. For details please refer to the Investigator's Brochure, section 5.3.6 ([c01715907-08](#)).

Proprietary confidential information.

© 2016 Boehringer Ingelheim International GmbH or one or more of its affiliated companies. All rights reserved.

This document may not - in full or in part - be passed on, reproduced, published or otherwise used without prior written permission.

The dose was planned to be escalated in cohorts at predefined dose levels based on a multiplication factor of approximately 3 in the low dose range (1-25 mg), a factor of 2 at doses of 25-800 mg and from the dose of 800 mg and onwards additional 200 mg per dose. The dose levels were initially planned to be: 1 mg, 3 mg, 9 mg, 25 mg, 50 mg, 100 mg, 200 mg, 400 mg, 800 mg, 1000 mg, 1200 mg and 1400 mg, however the MTD was established at 100mg based on safety data from Caucasian patients. An additional cohort of Korean patients will be tested at 50 and 75mg. Every time a dose-escalation is to be performed, all patients at the last cohort must have had 2 infusions of BI 836826 and at least 7 days observation after the second infusion. The available data of all previous dose cohorts will be reviewed. The data will be provided to the DSMB who will be asked to provide an independent assessment including the dose recommendation for the next cohort. As a result, lower dose increments than the predefined levels will be possible.

#### **4.1.4 Drug assignment and administration of doses for each patient**

Dose allocation will be controlled by the sponsor to ensure safety monitoring and the dose-escalation schedule is adhered to in the interest of the safety of the patients. In the dose-escalation phase there will be at least 7 days between first dose for patients in the same dose cohort and at least 14 days between first dose for last patient and first dose for first patient in different dose cohorts. Each investigational site must notify the sponsor when an eligible patient is identified. Prior to inclusion of a new patient during the dose-escalation phase the investigator has to confirm the actual dose tier of BI 836826 for the patient with the clinical monitor of the sponsor who oversees the dose-escalation steps and the safety data of patients from all trial sites. Enrollment will only be possible after the sponsor has notified the site by written confirmation of the dose and earliest possible date of first administration.

BI 836826 will be administered as an intravenous infusion under the supervision of the investigator or designated personnel.

BI 836826 may be administered at any time during the day. However, to facilitate blood sampling for and pharmacodynamic analyses, it is recommended to start the infusion during the morning hours.

